**Table 7 Vaccination time points**

Group	Visit 0 day -28	Visit 1 day 0	Visit 2 day 28	Visit 3 day 56	Visit 4 day 168	Visit 5 day 196	Visit 6 day 224	Visit 7 day 286
A, C	V/C		V/C			P		
B, D	P		V/C			V/C		
M1	C	V	V		P	P		
M2	C	P	P		V	V		

V = MV-CHIK vaccine (high or low dose), C = control-vaccine, P = placebo

The investigational medicinal products (IMPs) are described in detail in section 5.1, dosage and sequence ad 1.2, 1.3, 6.1 and Table 1, route of administration in section 5.3 and treatment period in section 8.4

## 9.2 Prior and concomitant therapy

### Permitted prior and concomitant therapy

Any prior vaccination within the last three years prior screening and any medication within 30 days prior screening have to be documented. Any medication taken during the study up to Visit 6 (study day 224) has to be reported to the investigator and has to be documented.

### Forbidden prior and concomitant therapy

Non-study licensed vaccines: vaccinations within 4 weeks prior to first vaccination and within 4 weeks after each study dose are not allowed.

Subjects have to be asked about concomitant medication and vaccinations at each visit; any concomitant medication or vaccination has to be documented.

## 9.3 Treatment Compliance

The study medication will be prepared at site and administered during the study visits. Each treatment will be documented in the subject's charts, the eCRF and an IMP Inventory Log (section 5.8)

## 10 ASSESSMENT OF IMMUNOGENICITY

### 10.1 Methods of Immunogenicity Measurements

#### Plaque reduction neutralization assay (PRNT50)

Humoral systemic immune response will be determined by anti-chikungunya neutralization assay. The 50% plaque reduction neutralization titer (PRNT50) will be measured to identify immunogenicity in sera of all subjects on days 0, 28, 56, 196 and 224 (treatment group A, B, C and D) and additionally on day -28 and 168 for treatment group M1 and M2. The assay will be validated and performed by SRI International (Harrisonburg, VA/USA).

#### Enzyme linked immunosorbent assay (ELISA)

In addition, humoral systemic immune response mediated by serum IgG antibodies against Chikungunya and against measles will be determined by IgG ELISA. CHIK-Ab will be determined on days 0, 28, 56, 196 and 224 (treatment group A, B, C and D) and additionally on day -28 and 168 for treatment group M1 and M2. Measles-Ab will be measured on days 0, 28 and 56 (treatment group A, B, C and D) and additionally on day -28 for treatment group M1 and M2. The assays will be validated and performed by the Department of Virology at the Medical University of Vienna, Austria.

#### T cell assay

Samples of a subset of subjects (all subjects enrolled in Vienna) will be analyzed for T cell immune response. PBMC from whole blood will be isolated to determine the number of functional, Chikungunya virus specific T cells on days 0, 28, 56, 196 and 224 (treatment group A, B, C and D) and additionally on day 168 for treatment group M1 and M2 (section 8.3.2). PBMC isolation and in vitro T cell assays will be performed by the Department of Virology, at the Medical University of Vienna. The functional T cell assays will be at research grade and will not be validated.

## 11 ASSESSMENT OF SAFETY

### 11.1 Data Safety Monitoring Board (DSMB) review

As the safety and tolerability profile of the vaccine was acceptable in a Phase 1 study in 42 healthy subjects, no major reactogenicity or safety findings are expected. Nevertheless, an independent external data safety monitoring board (DSMB) will be established by the study sponsor. The committee members will be experts in the field and they will not be involved in

the study in any other way. The purpose of the DSMB is to determine whether study or individual subject stopping rules have been met during ad-hoc meetings (teleconferences). The DSMB will periodically review listings and summary tabulations of SAEs, deaths, solicited AEs, unsolicited AEs and AEs leading to withdrawal from further vaccination in an unblinded manner. After about 50% of subjects completed Visit 3 (day 56) in groups A, B, C and D, the DSMB will review safety and immunogenicity in order to evaluate the risk-benefit of the MV-CHIK administration and make recommendations to the sponsor regarding the further study conduct and/or protocol modifications if needed.

In addition, the board will also review any SAE and "discontinuations" within a week after the event has been reported. In the case of an unexpected concern about potentially emerging safety problems, when a safety stopping rule is triggered, or when important new information external to the trial arises, a DSMB meeting will be scheduled. The DSMB will review unblinded data.

Detailed objectives, roles and responsibilities of the DSMB will be specified in a separate DSMB charter.

## **11.2 Post vaccination reactogenicity assessments**

Please also refer to Table 2 and section 8.2 for exact time points.

All subjects enrolled in the study and who receive at least one immunization (Priorix® or MV-CHIK) will be followed up for at least 28 days after the last immunization.

Adverse event rates will be used to evaluate the secondary study objective.

Serious adverse events: see below for detailed clarification

Medically attended adverse events: All adverse events, for which the subjects were seeking medical care (i.e. doctor's office, emergency service, hospital, but not use of self-medication).

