### 1.3 Visit procedures

**Table 2. Study Procedures**

Study Day	Screening Visit* Day -35*	Visit 0 Day -28	Visit 1 Day 0	Visit 2 Day 28	Visit 3 Day 56	Visit 4 Day 168	Visit 5 Day 196	Visit 6 Day 224	Visit 7 Day 286	Early Termination
Time windows / treatment groups	M1+M2: -35 to -29 A-D: -7 to -1	M1+M2: ±5 days **A-D -28 is study day 0	M1+M2 day 0 = V0+V1 at once on d 0	±5 days all groups	± 5 days all groups	±10 days only M1+M2	± 10 days all groups	± 10 days all groups	± 10 days all groups	
Informed consent	X									
Inclusion/exclusion criteria (1)	X	X	X (14)	X	X	X (14)	X			
HIV, hepatitis B/C, [blood: 8-10 mL]	X									
Demographic data	X									
Physical examination	X									
Vaccination history	X									
Hematology blood sample [3-5 mL] (6)	X				X			X		X
Coagulation parameter [blood: 3-5 mL] (7)	X				X			X		X
Clinical chemistry serum [8-10 mL] (8)	X				X			X		X
Urinalysis (10)	X				X			X		X
Medical history	X	X (2)								
Concomitant medications	X	X	X (14)	X	X	X (14)	X	X		X
Assessment of arthralgia	X	X	X (14)	X	X	X (14)	X	X		X
Symptom-directed physical exam (3)		X	X (14)	X	X	X (14)	X	X		X
Vital signs (4)	X	X	X (14)	X	X	X (14)	X	X		X
Urine pregnancy test (9)	X	X	X (14)	X	X	X (14)	X	X	(15)	X
Randomization		M1+M2 X	A B C D							
Study treatment: vaccination		X (14)	X	X		X (14)	X			
Immunogenicity 1: serum [blood: 2x 8-10 mL]		X (14)	X	X	X	X (14)	X	X		X
Immunogenicity 2 (5.1): [blood: 16-20 mL]		X (14)	X	X	X	X (14)	X	X		X
Measles antibody titer [no additional blood sample]		X (14)	X	X	X					X
T- cell analysis (5.2): [blood: 24-30 mL]			X	X	X	X (14)	X	X		X
Measles virus shedding (13): [blood: 2-3 mL, urine and saliva]			X (13)	X (13)			X (13)			
Local tolerability (12)		X (14)	X	X	X	X (14)	X	X		X
Dispense subject diary (11)		X (14)	X	X		X (14)	X			
Collect subject diary (11)			X (14)	X	X		X (14)	X		X
Adverse events		X (14,2)	X (2)	X	X	X (14)	X	X		X

\* Screening visit within 7 days before randomization

(1) After randomization only exclusion criteria, which could influence the subject's eligibility throughout the study will be checked. The following exclusion criteria are concerned: 1, 7, 8, 10, 19, 20, 21, 22 and 23

(2) Symptoms noted prior to randomization are not considered as adverse events but will be recorded as medical history

(3) Including system-based assessment if necessary according to symptom-directed physical examination. (section 11.2.2)

(4) Systolic and diastolic blood pressure, body temperature and pulse

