### **8.2.6 Study day 196 ( $\pm 10$ days) / Visit 5**

All subjects will return to the study sites for an outpatient visit. The inclusion/exclusion criteria will be checked again. Symptom-directed physical exam, system-based assessment (only if necessary according to symptom-directed physical exam) and evaluation of vital signs as well as body temperature will be recorded. For subjects of group M1 and M2 an assessment of local tolerability (of previous vaccination site) will be done and subject diaries will be collected and checked for completeness. Blood samples for immunogenicity 1 will be obtained, a urine pregnancy test will be performed in women of childbearing potential and all study sites except the two sites in Vienna will collect serum samples for cross neutralization and passive transfer analyses (immunogenicity 2). In addition, the subjects will be asked if they experience any kind of arthralgia. Adverse events and concomitant medication will be recorded, if applicable.

Subjects of all groups will receive their last vaccination (group A-D the 3rd and group M1 + M2 the 5th vaccination) and will be observed for 1 hour after each vaccination before discharge from study site. One hour after vaccination local tolerability and adverse events, if applicable, will be recorded.

The last subject diary will be dispensed and the subjects will be asked to report any adverse events in the diary for 7 days after vaccination. Adverse events and concomitant medication will be recorded, if applicable.

Subjects will be asked to return to the study site after 28 days on study day 224 ( $\pm 10$  days) for the last Visit 6.

Vienna sites only:

For T cell assays a total of 24-30 mL blood (3x 10 mL citrate tubes) will be collected from all subjects enrolled at these sites.

AKH Vienna only:

Virus shedding samples (urine, saliva and whole blood) will be collected from a subset of subjects randomized to treatment group A-D.

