### **8.2.8 Study day 286 ( $\pm 10$ days) / Visit 7**

All women of childbearing potential will be followed up 3 months after the last vaccination to ensure that no pregnancy occurred within this period. This will be done via a phone call on study day 286 (or in case of prematurely discontinuation of the study for any reason, 3 months after the subject received the last vaccination). The subject will be asked about the result of the provided pregnancy urine test.

Additionally, subjects will be advised to immediately inform the investigator of pregnancies up to 6 months after the last vaccination also if this occurs after this follow up call.

If a subject has become pregnant since the last visit this has to be reported as defined under 14.7 and will be followed until pregnancy outcome.

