### 13.2 Safety Analysis

Solicited AEs (reactogenicity): Solicited local and solicited systemic AEs will be summarized for the 7 day period, by AE grade (mild, moderate, severe), by group and by dose. Solicited AEs will not be coded into MedDRA or assessed for relatedness. The number and percentage of subjects with AEs will be presented. Subjects who reported data for a solicited event at any time point during the time period summarized would be included in the denominator for that event. Thus, denominators for each solicited event will not include subjects who were missing all data for that event, during the time period summarized. P-values for AE rates for MV-CHIK vs. Priorix® (or equal control-vaccine), for the same schedule, will be provided in summary tables (pairwise comparisons).

Unsolicited AEs: Separately, the number and percentage of subjects with unsolicited treatment emergent adverse events (TEAEs), medically-attended AEs (MAEs) and serious adverse events (SAEs) will be presented for each treatment group overall and by system organ class/preferred term, and by AE grade, and relatedness. All SAEs and MAEs are also included in TEAE tables. Arthritis AEs, AEs of special interest (AESI), will be included in the TEAE tables. For unsolicited AEs, all subjects entered into the study who receive at least one vaccination will be included in the safety analysis based on the product received (“as treated”), for the time period summarized. P-values for AE rates for MV-CHIK vs. Priorix®, for the same schedule, will be provided in summary tables (pairwise comparisons).

Unsolicited AEs and concomitant diseases will be coded using the MedDRA coding dictionary; concomitant medications will be coded using the WHO Drug Dictionary.

Solicited and unsolicited AEs (local and systemic), MAE, SAE and AESI (arthralgia) will be recorded up to Visit 6 (day 224).

Safety analyses will be performed by means of descriptive measures. Laboratory values will be assigned a grade. Changes in laboratory values and grades as well as vital signs from study entry to end of treatment/follow up will be analyzed descriptively.

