## 14.5 Collection, Recording and Reporting of Adverse Events

All events meeting the definition of an Adverse Event must be collected and reported starting with randomization (Visit 0/ day -28) until the end of the protocol required post-treatment follow-up period (Visit 6 28 days after the last vaccination).

At each contact to the site (visit or telephone, excluding safety visits) where the subject is not seeing the investigator or his staff (e.g. visits to the laboratory), the subject must be asked about adverse events. All adverse events either observed by the investigator or reported by the subject must be recorded by the investigator and evaluated.

The subjects will be asked in general: "How are you?" as well as specifically: "Have you experienced any problems since the last contact?"

The investigator should record the diagnosis, if available. If no diagnosis is available, the investigator should record each sign and symptom as individual adverse events.

The investigator must record all adverse events in the eCRF. One single adverse event line must be used per adverse event, from start to resolution. For serious adverse events, the Serious Adverse Event Report Form must also be completed.

The investigator must report all SAEs with the completed SAE Report Form within 24 hours after learning of its occurrence to:

Assign Safety Desk: [contact]

Email: [[contact]](mailto:[contact])

For urgent questions please call the 24-hours Safety [contact]**

Under certain circumstances the first notification can be done by phone; nevertheless, a written Serious Adverse Event Report Form has to be submitted for confirmation to Assign Safety Desk. Reporting timelines are applicable also if the SAE is not felt to be treatment-related. The monitor must be informed accordingly.

The original copy of the SAE Report Form and the fax confirmation sheet must be kept with the documentation at the study site.

Please note: Each SAE has also to be documented in the eCRF as a serious adverse event in the corresponding AE section.

The sponsor is responsible to fulfill the requirements of expedited reporting of all SUSARs (Suspected Unexpected Serious Adverse Reaction) to the Competent Authorities, Ethics Committees and principal investigators concerned according to national and European law and regulations.

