## 14.6 Follow-up of Adverse Events

During and following a subject's participation in a clinical trial, the investigator/institution will ensure that adequate medical care is provided to the subject for any adverse events, including clinically significant laboratory values related to the trial. The investigator/institution will inform the subject when medical care is needed for adverse event(s) of which the investigator becomes aware. All non-serious adverse events classified as severe or definitely/possibly/probably related to the trial product must be followed until 28 days after the administration of MV-CHIK or control (vaccine or placebo). All serious adverse events must be followed until the subject has recovered, stabilized, recovered with sequelae or died.

All other adverse events must be followed until the subject has recovered or stabilized or until the end of the protocol required post-treatment follow-up whichever comes first, and until all adverse event related queries for the subject have been resolved.

Follow-up information about a previously reported SAE must also be reported within 24 hours of the investigator receiving it. The initial SAE report form should be used, stating that this is a follow-up report to the previously reported SAE and giving the date of the follow-up report. The information provided should describe whether the event has resolved or continues, if and how it was treated, and whether the subject continued or discontinued study participation, if not already stated in the initial report.

The original copy of the SAE form including any follow-up information and the fax confirmation sheet must be kept with the documentation at the study site.

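### The 28-day adverse event endpoint is not tabulated as defined, and the Visit 6 window does not secure the promised 28 days of follow-up after an active dose on Day 196

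*Protocol*

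**What the plan says.** **The endpoint.** Protocol 4.1.2 and SAP 1.3.2 both list, as a secondary endpoint, the rate of AEs in the 28 days after vaccination. SAP 2.17 declares no change to the planned analysis other than the date of the preliminary analysis.

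**The tables.** SAP 8.3 summarises solicited AEs over 7 days. It treats an unsolicited AE as treatment-emergent if it starts or worsens at or after the first vaccination, and sets no end. In the list of tables (SAP 10.1), none of tables 4.2 to 4.11 is restricted to a period after a dose. The preliminary analysis takes AEs that start up to Visit 3.

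**The follow-up.** Protocol 11.2 says that subjects who receive Priorix or MV-CHIK "will be followed up for at least 28 days after the last immunization". It adds: "Please also refer to Table 2 and section 8.2 for exact time points". Table 2 gives Visit 6 (Day 224) a tolerance of ± "10 days all groups". At Visit 5 subjects are asked to "return to the study site after 28 days on study day 224" (8.2.6), again with ±10 days. Section 13.2 sets the end of recording: "Solicited and unsolicited AEs (local and systemic), MAE, SAE and AESI (arthralgia) will be recorded up to Visit 6 (day 224"). Section 14.5 also ends collection there and describes the visit as "Visit 6 28 days after the last vaccination".

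**The concern.** Safety of the MV-CHIK booster 24 weeks after primary immunization is a named secondary objective (Protocol 3.2). In groups B and D the two MV-CHIK doses are 168 days apart, whereas the Phase 1 study gave the second dose only on Day 28 or Day 90 (Protocol 2.4). The 28-day AE rate after the Day 196 dose is thus information that this trial is meant to supply for the first time.

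Two things stand in the way. The planned tables do not isolate that rate from events far from any dose. And a subject can attend Visit 6 within its window and still have less than 28 days of AE recording after the last active dose. No planned table would show how many subjects had the full period.

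**Working it through.** **1. What the final unsolicited tables cover (nominal days).** Assumption: the first vaccination means the first injection, placebo included, as in the SAP's numbering of vaccinations (2.13).
- Groups A to D: injections on Days 0, 28 and 196; recording to Day 224. Span 224 − 0 = 224 days. The 28-day periods after the three injections cover 3 × 28 = 84 days. Outside any such period: 224 − 84 = 140 days, or 140/224 = 62.5% of the span.
- Groups M1 and M2: injections on Days −28, 0, 28, 168 and 196. Span 224 + 28 = 252 days; covered 5 × 28 = 140; outside 252 − 140 = 112 days, or 112/252 = 44%.
- In M2 the count starts at Priorix on Day −28, which is 168 + 28 = 196 days before the first MV-CHIK dose on Day 168.

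The whole-study rate is therefore a different quantity from the 28-day rate, and the second cannot be read from the first.

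**2. What the preliminary cut covers.** Up to Visit 3 (Day 56) it spans the 28-day periods after Days 0 and 28, and after Day −28 for M1 and M2. These are pooled, not shown by dose. The Day 168 and Day 196 injections lie outside it. SAP 2.17 also brings this analysis forward to August 2017, so it need not include every subject's Visit 3.

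**3. Length of recording after the last active dose.** The plan's own figure reproduces: 224 − 196 = 28 days. Counting the ±10-day window from the Visit 5 injection:
- Earliest Visit 6: 28 − 10 = post-dose day 18.
- Unrecorded at most: days 19 to 28, that is 28 − 18 = 10 days per subject.
- Latest Visit 6: 28 + 10 = post-dose day 38.

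**4. Who is concerned** (Protocol Table 1):
- MV-CHIK on Day 196: B 60 + D 60 + M2 20 = 140.
- Control vaccine on Day 196: 10 in B + 10 in D = 20.
- Total 160 of 320, or 50%. Of these, 60 + 60 = 120 receive the 24-week MV-CHIK booster (196 − 28 = 168 days = 24 weeks).
- Groups A and C, their controls, and M1 have their last active dose on Day 28. Recording then runs 224 − 28 = 196 days nominally, so no shortfall arises.

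**5. Whether another provision restores the 28 days.** Section 14.6 says that severe or related non-serious AEs "must be followed until 28 days after the administration of MV-CHIK or control (vaccine or placebo"). This governs events already known and does not extend collection of new ones. Visit 7 (8.2.8) is a telephone call to women of childbearing potential; of this call the protocol says: "The subject will be asked about the result of the provided pregnancy urine test". Table 2 marks no AE assessment for it, and the SAP's Austrian visit schedule (1.5.3) has no Visit 7.

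**The case against.** The strongest reply is that every section describes the same plan: inject on Day 196, return 28 days later. Section 11.2 itself sends the reader to Table 2 and section 8.2, where an ordinary symmetric visit window is given. On this view the phrase in 11.2 is loosely worded, and nobody intends to stop safety follow-up early. That is right about intent and about the nominal schedule. It does not supply the minimum that 11.2 states, because recording closes at the visit and the visit may be early.

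Second, section 14.5 says that subjects must be asked about AEs at site contacts, including by telephone, so the Visit 7 call might pick up events. It would be wrong to say that the call can concern nothing but pregnancy. It still leaves out men and women not of childbearing potential, and formal collection has ended by then.

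Third, much of what is needed is already planned. Diary reactogenicity is tabulated by injection, including the one on Day 196 (SAP 2.13 and 10.1). The Visit 3 cut nominally covers the early 28-day periods. Listings 1.5, 4.1 and 4.2 give visit and vaccination dates. A reader might infer that the SAP ignores the post-dose period altogether; it does not. What remains missing is a 28-day table for unsolicited AEs, by dose, that includes the later injections.

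**Conclusion.** The concern holds in two limited parts.

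The first does not depend on attendance: the SAP names a 28-day AE rate and does not tabulate it as defined. The gap matters most for the Day 168 and Day 196 doses, which no 28-day or preliminary summary of unsolicited AEs reaches.

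The second is conditional: for 160 planned subjects the plan permits up to 10 of the 28 days after the last active dose to go unrecorded. The documents give no attendance data, so the number affected lies between 0 and 160. Only new unsolicited events late in the period, serious ones included, are exposed. The 7-day diary, follow-up of known severe or related AEs and of SAEs, and the Day 56 primary analysis are untouched.

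Four stronger readings are not supported:
- That about a third of the follow-up will be lost. The ratio (160 × 10)/(160 × 28) = 1,600/4,480 = 36% needs every subject to attend on the first permitted day. It is a ceiling, not an estimate.
- That recording may stop on day 8, by setting a late Visit 5 against an early Visit 6: (224 − 10) − (196 + 10) = 8. Sections 8.2.6 and 14.5 count Visit 6 as 28 days from the last injection, so this reading fits the text poorly.
- That the comparison of MV-CHIK with Priorix is biased. Arms on the same schedule share the same window.
- That the planned AE rates must be too low. Early closure can only lower a strict 28-day rate, but the planned tables have no cap, and subjects attending as late as day 38 add events to them.

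**What to change.** **SAP.** Add one table of unsolicited AEs with onset from each injection to day 28 or the next injection, whichever comes first. Assign each AE to the most recent injection, so that no event is counted twice when the visit windows bring two doses closer than 28 days. Show it by treatment group and dose, with the number of subjects observed for the full 28 days after the last active dose. The vaccination, visit and AE start dates are already in the planned listings (SAP 10.2), so no new data are needed, even if Visit 6 is complete.

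**Protocol, if Visit 6 is still to come.** In 13.2 and 14.5, record AEs up to Visit 6 or day 28 after the actual last injection, whichever is later. Add a telephone AE contact when Visit 6 falls before day 28.

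**Cost.** One derived variable, one table, an occasional call and a minor amendment. The amendment needs ethics committee approval (Protocol 17.1) and would have to be made in both country protocols on which the SAP rests (SAP 2). As the SAP is dated May 2018, the protocol change may come too late; the SAP change stands on its own.
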